### 9.2.2 Treatment Grouping

Period will refer to the analysis (treatment) period, as opposed to study period. This means that Study Period 2 will be divided in two analysis periods, Analysis Period 2 (Days -1 to 6) and Analysis Period 3 (Days 7 to 16). The study will therefore consist of 3 analysis periods. For Analysis Period 3, the analysis day will also be adjusted by subtracting 6 from the study day. Thus, Period 3 will have Analysis Days 1 to 10.

Label	Grouping
Analysis Period	
Study Drug	Balovaptan (reference), rifampicin, balovaptan + rifampicin (test)
Treatment	Treatment S: 10 mg balovaptan Treatment I: 600 mg rifampicin Treatment S+I: 10 mg balovaptan + 600 mg rifampicin

S= Substrate, I= Index Inducer

### 9.2.3 Common Variable Derivations

Variable	Data Type	Definition/Calculation	Note
Change from Baseline	All	Post-dose Observation minus Baseline Observation	
Analysis Period	All	Time period starting 1 day before dosing of each of the treatments and ends 1 day before dosing in next analysis period or at the start of the follow-up period for the last treatment.	
Analysis Study Day (Prior to Dose)	All	Date of Measurement minus Dose Date	
Analysis Study Day (Post Dose)	All	Date of Measurement minus Dose Date +1	

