#### Study Period 2:

- Days 1 to 6: rifampicin 600 mg qd
- Days 7 to 16: balovaptan 10 mg qd + rifampicin 600 mg qd

Figure 1 presents an overview of the study design.

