  - b A standardized breakfast will be provided at least 30 minutes after dosing of balovaptan alone, rifampicin alone, or balovaptan + rifampicin together in either period. A standardized lunch and standardized dinner will be provided 4 and 10 hours post dose, respectively, in both periods. Standardized afternoon and evening snacks will be provided as well.
  - c Samples to measure the concentration of balovaptan, M2, and M3 (one sample per time point to measure all 3 analytes) will be taken at predose, and 0.5, 1, 1.5, 2, 2.5, 3, 4, 6, 8, 12, 16, 24, hours post dose on Days 10/11 of Period 1 (16- and 24-hour samples are on the morning of Day 11) and 16/17 of Period 2 (16- and 24-hour samples are on the morning of Day 17). A predose sample to measure the concentration of balovaptan, M2, and M3 will also be taken on Days 2, 4, 8, and 9 in Period 1, and on Days 8, 10, 14, and 15 in Period 2 (see also [Appendix 2](#)).
  - d Samples to measure the concentration of rifampicin will be taken predose and at 1, 1.5, 2, 3, 4, 6, 12, and 24 hours post dose of rifampicin on Days 6/7 and 16/17 of Period 2 (24-hour samples are on the morning of Days 7 and 17) (see also [Appendix 2](#)).
  - e Includes measurement of height, weight and BMI.
  - f Includes measurement of weight.
  - g Triplicate ECGs will be collected as follows: in Period 1, on Day -1 and predose and 3 hours after dosing of balovaptan on Days 3, 7, and 10 and in the morning of Day 11; and in Period 2, on Day -1, and predose and 3 hours post dose on Days 3, 6, 9, 13, and 16; in the morning of Day 17, and at Follow-up (see also [Appendix 2](#)).
  - h Vital signs will be collected as follows: in Period 1, on Day -1 and predose and 3 hours after dosing of balovaptan on Days 3, 7, and 10 and in the morning of Day 11; and in Period 2, on Day -1, and predose and 3 hours post dose on Days 3, 6, 9, 13, and 16; in the morning of Day 17, and at Follow-up (see also [Appendix 2](#)).
  - i Includes measurement of body temperature.
  - j Hematology and chemistry at Screening and on Days -1 and 11 of Period 1 and on Days -1, 3, 6, 9, 13, 17 in Period 2, and follow up. Urinalysis at Screening and on Days -1 and 11 of Period 1 and on Days -1 and 17 in Period 2 and at Follow-up.
  - k For females only: FSH and serum pregnancy test at Screening, and serum pregnancy test only at all other time points.

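### SAP 9.2.3 starts the combination analysis period on Day 6 of Study Period 2, a rifampicin-alone dosing day, and so contradicts SAP 9.2.2 on the treatment label of Day 6 data

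*SAP*

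**What the plan says.** The dosing schedule for Study Period 2 in SAP section 6.0 is "Days 1 to 6: rifampicin 600 mg qd", then "Days 7 to 16: balovaptan 10 mg qd + rifampicin 600 mg qd". No drug-free day separates the two treatments.

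SAP 9.2.2 splits Study Period 2 into "Analysis Period 2 (Days -1 to 6) and Analysis Period 3 (Days 7 to 16"). It subtracts 6 from the study day in the later part and gives the result: "Thus, Period 3 will have Analysis Days 1 to 10".

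SAP 9.2.3 defines the same variable again, for every data type, as "Time period starting 1 day before dosing of each of the treatments and ends 1 day before dosing in next analysis period". For the last treatment, the period closes when follow-up starts.

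The footnotes to SAP Appendix 2 place these assessments on Day 6 of Study Period 2:

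- ECG and vital signs: "predose and 3 hours post dose on Days 3, 6, 9, 13, and 16".
- Haematology and chemistry: "on Days -1, 3, 6, 9, 13, 17 in Period 2".
- Rifampicin PK on Days 6/7 and 16/17: "Samples to measure the concentration of rifampicin will be taken predose and at 1, 1.5, 2, 3, 4, 6, 12, and 24 hours". The 24 h sample of the first profile is drawn on the morning of Day 7.

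**The concern.** A period that opens on the day before dosing works when that day is drug-free, as Day -1 is in both study periods. It does not work at the change from rifampicin alone to the combination, because the day before the first combination dose is the sixth rifampicin-alone dosing day. The SAP therefore gives the same Day 6 records two different period assignments.

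The period sets the treatment label, and SAP 9.1.4 calculates summary statistics by treatment. Under 9.2.3, values taken before any balovaptan dose in Study Period 2 can appear under balovaptan + rifampicin, and one of the two on-treatment safety days can drop out of the rifampicin-alone column. Safety of balovaptan alone and in combination is a secondary objective. The baseline in SAP 9.2.1 is also tied to the first drug administration in each period, so it can move with the boundary.

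**Working it through.** The check is day arithmetic; no power or precision formula applies.

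**1. Reproduce the plan's figure.** Subtracting 6 from Study Days 7 to 16 gives 7 − 6 = 1 and 16 − 6 = 10. This matches the Analysis Days 1 to 10 stated in 9.2.2.

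**2. Apply 9.2.3.** The first rifampicin-alone dose is on Day 1 and the first combination dose on Day 7; there is no Day 0. One day before Day 1 is Day -1, so Analysis Period 2 starts there, as in 9.2.2. One day before Day 7 is 7 − 1 = Day 6, so Analysis Period 3 starts on Day 6.

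| Rule | Analysis Period 2 | Analysis Period 3 starts | Day 6 falls in |
|---|---|---|---|
| 9.2.2 | Days -1 to 6 | Day 7 | Period 2 only |
| 9.2.3, end day excluded | Days -1 to 5 | Day 6 | Period 3 only |
| 9.2.3, end day included | Days -1 to 6 | Day 6 | both |
| 9.2.3, clock time | up to the Day 6 dose time | 24 h before the Day 7 dose | Period 3 from the dose onward |

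No reading of 9.2.3 gives the 9.2.2 split. The clock-time row assumes the same dosing time each morning.

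**3. Analysis day.** For a record before dosing, 9.2.3 takes measurement date minus dose date. For Day 6 in Analysis Period 3 this is 6 − 7 = −1, outside the stated range of 1 to 10.

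**4. Count the records.**

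- ECG and vital signs: the rifampicin-alone dosing days with measurements are Days 3 and 6, each pre-dose and at 3 h, so 4 time points. Day 6 holds 2 of 4. On the clock reading only the 3 h measurement moves, 1 of 4.
- Haematology and chemistry: Days 3 and 6, so 1 of 2 on-treatment samples.
- Rifampicin concentrations: the Day 6/7 profile has 9 samples. By calendar day, 8 (pre-dose to 12 h) fall on Day 6 and are labelled differently by the two sections. The ninth, at 24 h on Day 7, falls in Analysis Period 3 under both. On the clock reading, the 8 samples from 1 h to 24 h fall in Analysis Period 3.

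**5. Baseline.** Take vital signs, with no unscheduled readings. Under 9.2.2 the first administration in Analysis Period 3 is the Day 7 dose, so the baseline is the Day 6 reading at 3 h. If Analysis Period 3 opens on Day 6, its first administration can be read as that day's rifampicin dose, and the baseline becomes the Day 6 pre-dose reading. For haematology and chemistry the documents give no hour for the Day 6 sample. If it is drawn after the dose, the same reading moves the baseline back to Day 3. ECG baseline is fixed to Analysis Period 1 and urinalysis is not collected on Day 6, so neither moves.

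**The case against.** The strongest reply is that 9.2.2 is the study-specific rule. It names the days, the shift and the resulting range, whereas 9.2.3 is a generic line in a table of common derivations. On an inclusive reading, the end clause of 9.2.3 also agrees with 9.2.2 that Analysis Period 2 runs to Day 6, so only the start clause conflicts. A careful programmer would probably follow 9.2.2 for Day 6.

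That is fair, but the SAP does not require it, and 9.2.2 is not sufficient alone. It stops Analysis Period 3 at Day 16, although ECG, vital signs, haematology, chemistry and urinalysis are collected on Day 17; only 9.2.3 carries the period to follow-up. By calendar day, 9.2.2 also puts the Day 7 24 h rifampicin sample in the combination period, although it completes the rifampicin-alone profile.

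A reader might infer that rifampicin-alone data in general would be reported as combination data. The documents do not support that:

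- The primary comparison uses balovaptan, M2 and M3 on Day 10 of Period 1 and Day 16 of Period 2.
- SAP 17.1.1 attributes AEs from dose to dose, to the last treatment received.
- SAP Table 1 names the rifampicin parameters by Day 6, and SAP 5.3.1 and Figure 1 identify the profiles by day.
- Laboratory, vital-sign and ECG tables are split by scheduled time, so a mislabelled Day 6 is a separate row and is not averaged into Days 9, 13 and 16.

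Double programming of the PK datasets (SAP 9.2.4.1) would probably expose divergent readings of rifampicin concentrations. The laboratory, vital-sign and ECG datasets are not on that list, and no table shells are planned.

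**Conclusion.** The contradiction is real and follows from the text alone: 9.2.3 starts the combination period on Day 6, and 9.2.2 starts it on Day 7. It would be too strong to say that 9.2.3 places Day 6 solely in the combination period, since the inclusive reading places it in both.

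The effect is limited to three things: the treatment label of the Day 6 ECG, vital-sign, haematology and chemistry rows, which are one of two on-treatment safety days for rifampicin alone; the treatment label of up to 8 of the 9 samples of the first rifampicin profile in the concentration summary; and the Period 3 baseline for non-ECG safety data. These are descriptive outputs, and individual values are also listed. The point deserves correction before database lock but does not threaten the primary result.

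This rests on the assessment days in the Appendix 2 footnotes, and on the Day 7 24 h rifampicin sample being drawn before that morning's dose.

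**What to change.** Amend 9.2.2 and 9.2.3 together:

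- Analysis Period 2 ends, and Analysis Period 3 starts, at the first balovaptan + rifampicin dose on Day 7 of Study Period 2.
- All Day 6 assessments, and all Day 7 samples taken before that dose, including the 24 h rifampicin sample, belong to Analysis Period 2.
- Opening a period on the day before dosing applies only to Analysis Periods 1 and 2.
- Analysis Period 3 still closes at the start of follow-up, so that Day 17 data have a period.

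The first administration in Analysis Period 3 is then the Day 7 dose, which also settles the 9.2.1 baseline. Changing 9.2.3 alone would leave 9.2.2 assigning all of Day 7 to Analysis Period 3. The cost is a few sentences in the SAP before database lock; data collection, study conduct and the primary model do not change.

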### 9.2.4 QC

The analysis datasets and the TFLs will be QC'd according to the general PRA EDS QC plan.

#### 9.2.4.1 Critical Data

The QC plan requires datasets be classified as critical or non-critical. As the primary objective of this study is to characterize the PK the datasets considered critical are subject level and PK (ADSL, ADPC, ADPP). As these are related to the primary objectives these datasets will be double programmed per the QC Plan.

### 9.2.5 ADaM Datasets and Metadata

The analysis datasets will be generated in accordance with Clinical Data Interchange Standard Consortium (CDISC) Analysis Data Model (ADaM) Version 2.1. At least the following datasets will be created:

- ADSL
- ADAE
- Laboratory Analysis Dataset (ADLB)
- Vital Signs Analysis Dataset (ADVS)
- ECG Analysis Dataset (ADEG)
- ADPC
- ADPP

ADaM compliant datasets will be delivered to the sponsor. A define.xml file Version 2 with the corresponding metadata will be included. Analysis results metadata are excluded.

## 9.3 Software

The statistical analysis and reporting will be done using SAS® for Windows™ Version 9.4 or higher (SAS Institute, Inc.).

PK parameter calculations will primarily be done using Phoenix® WinNonlin® Version 8.1 or higher (██████████). Additional PK computations may be performed in SAS®.

---

## 9.4 Statistical Methods

### 9.4.1 Statistical Outlier Determination

No statistical outlier analysis is planned.

### 9.4.2 Predetermined Covariates and Prognostic Factors

CYP3A4 genotype will be investigated as a factor in this study. PK tables will be presented by CYP3A4 genotype.

The pharmacogenetics of other isoforms, metabolizing enzymes, transferases, transporters, etc, possibly involved in the absorption, distribution, metabolism and excretion of balovaptan and its major metabolites (e.g., CYP3A and P-glycoprotein) may be investigated additionally (e.g. CYP3A5 genotype).

### 9.4.3 Hypothesis Testing

No formal hypothesis testing will be done.

## 9.5 TFL Layout

Report layout will be according to the PRA EDS – ICH E3 compliant – CSR Template. The layout of TFLs will be according to the PRA EDS standards.

No table shells will be provided. The TFLs will be provided in Adobe PDF format.

Format:

- Page size: A4
- Data in listings will be sorted by subject number and time point.
- Data in tables will be sorted by treatment and time point.
- Column titles will be in title case letters.
- All tables and listings will be in landscape format.
- The treatment labels will be as outlined in Section 9.2.2 Treatment/Subject Grouping Definition

## 10.0 Analysis Populations

Analyses	Safety	Pharmacokinetic
Disposition Summaries	✓	
Safety Assessments	✓	
Baseline Characteristics	✓	✓
Primary Analysis		✓
PK Concentrations		✓
PK Parameters		✓

### 10.1 Safety Analysis Population

The safety set will consist of subjects who receive at least one dose of balovaptan. This set will be used for the safety data summaries and baseline characteristic summaries.

### 10.2 Pharmacokinetic Analysis Population

The PK set will consist of all subjects who receive at least 1 dose of balovaptan. Subject will be excluded from the PK set if they significantly violate the inclusion or exclusion criteria, deviate significantly from the protocol, or if data are unavailable or incomplete. Excluded cases will be documented together with the reason for exclusion in the CSR. All decisions on exclusions from the analysis will be made prior to database closure.

## 11.0 Subject Disposition

The number and percentage of subjects randomized, dosed, and members of each analysis set will be presented. The number and percentage of subjects who withdrew from the study prematurely and a breakdown of the corresponding reasons for withdrawal will also be presented. If the reason for discontinuation is "other", further specifications will only be listed.

## 12.0 Protocol Deviations and Violations

Protocol deviations/violations will be included in the CSR.

## 13.0 Demographic and Baseline Characteristics

### 13.1 Demographics

All demographic data as collected during the screenings visit will be listed by subject. Genotype information will be included.

Subject demographics will be summarized descriptively for all subjects by genotype and overall. The summary will include the subjects' age (in years), gender, race, ethnicity, weight (in kg), height (in cm), and BMI (in kg/m^2). Demographics will be summarized for the safety and (if necessary) for the PK sets.

## 13.2 Medical History

Medical history will be listed including the coding according to the Medical Dictionary for Regulatory Activities (MedDRA; latest version).

## 13.3 Other Baseline Characteristics

- Drug and alcohol screen: The results of urine drug screen (barbiturates, benzodiazepines, methadone, amphetamines [including ecstasy], methamphetamines, opiates, cocaine, and cannabinoids and urine alcohol test will be listed.
- Serology: The results of serology (human immunodeficiency virus (HIV)-1 and HIV-2, hepatitis B virus surface antigen (HBsAg), hepatitis C virus (HCV) antibody) at screening will be listed.
- Pregnancy test (females only): Serum pregnancy test results (beta-human chorionic gonadotropin) and follicle-stimulating hormone (FSH) will be listed for each female subject at screening, each admission to the clinical research center and at follow-up.
- Body weight will be listed at screening and at follow-up.
- Non-compliance to in- or exclusion criteria (if any) will be listed.

## 14.0 Concomitant Medications

Concomitant medications, categorized by medication group and subgroup according to GNE Drug dictionary, will be summarized. The number and percentage of subjects using each medication will be displayed with the number and percentage of subjects using at least one medication within each medication group and subgroup, by treatment.

Concomitant medication will be listed. Medications with an end date prior to the first dose of study drug will be considered prior medications and will be noted in the listing. If a partial date allows a medication to be considered concomitant it will be categorized as such.

## 15.0 Treatment Compliance and Exposure

Exposure data will be listed by subject.

The number of subjects receiving each dose of study drug will be summarized.

## 16.0 Pharmacokinetic Analyses

PK concentrations will be collected in plasma.

### 16.1 Pharmacokinetic Variables

#### 16.1.1 Concentrations

- Plasma concentration of balovaptan
- Plasma concentration of metabolite M2
- Plasma concentration of metabolite M3
- Plasma concentration of rifampicin

#### 16.1.2 Parameters

- PK Parameters for balovaptan, M2, M3 and rifampicin as defined in [Table 1](#).

**Table 1: Plasma Parameters**

Parameter	Description	Analyte/ Analysis Day	SAS Programming Notes
C max	Maximum plasma concentration. Observed peak analyte concentration obtained directly from the experimental data without interpolation, expressed in concentration units	All analytes/ Analysis Day 10 (or Day 6 for rifampicin)	Cmax from WNL
C trough	Concentration at the end of the dosing interval (tau)	All analytes	The concentration at 24 h calculated in SAS
t max	Time to maximum plasma concentration. First observed time to reach peak analyte concentration obtained directly from the experimental data without interpolation, expressed in time units.	All analytes/ Analysis Day 10 (or Day 6 for rifampicin)	Tmax from WNL
AUC 0-last	Area under the concentration-time curve (time 0 to time of last quantifiable concentration).	Rifampicin/ Analysis Day 6	AUClast from WNL
AUC 0-24h	Area under the serum concentration-time curve from time 0 to 24 hours post-dose	All analytes/ Analysis Day 10 (or 6 for rifampicin)	AUC0-24 from WNL where partial time =24, if missing for a subject then AUC at nominal time 24 hr from summary file is used for AUC0-24
λ z	Terminal phase rate constant calculated by linear regression of the terminal log-linear portion of the concentration vs. time curve. Linear regression of at least three points and an adjusted R  greater than 0.70 are required to obtain a reliable λ z .	All analytes/ Analysis Day 10 (or 6 for rifampicin)	Lambda_z from WNL If adjusted R  ≤ 0.7 the parameter is not estimated
t 1/2	Terminal phase half-life expressed in time units. Percent extrapolation <20% and adjusted R  greater than 0.7 is required to obtain a reliable t 1/2 .	All analytes/ Analysis Day 10 (or 6 for rifampicin)	HL_Lambda_z from WNL If adjusted R  ≤ 0.7 the parameter is not estimated
MR_C max	Metabolite to parent (balovaptan) ratio of C max	M2, M3	Cmax (metabolite)/ Cmax (parent) from WNL *Corrected for molecular weight.
MR_AUC 0-24h	Metabolite to parent (balovaptan) ratio of AUC 0-24h	M2, M3	AUC0-24 (metabolite)/ AUC0-24 (parent) from WNL *Corrected for molecular weight.

Note: AUCs will be calculated using linear up / log down, expressed in units of concentration x time.

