2. OBJECTIVES AND ENDPOINTS

This study will investigate the effect of rifampicin treatment on the PK of balovaptan and its major metabolites M2 and M3. [Table 1](#) presents the objectives and endpoints.

Table 1 Objectives and Corresponding Endpoints

Objectives	Endpoints
Primary	
To investigate the effect of multiple doses of rifampicin, a potent CYP3A4 inducer, on the pharmacokinetics of balovaptan 10 mg qd and its major metabolites M2 and M3 at steady state in healthy subjects	Primary PK endpoints: C_{max} and area under the concentration curve from time 0 to 24 hours (AUC_{0-24h}) for balovaptan, M2, and M3 following 10 days of qd dosing of balovaptan 10 mg

Secondary	
To evaluate the safety and tolerability of balovaptan 10 mg qd administered alone and in combination with rifampicin in healthy subjects	AEs, clinical laboratory values, vital signs, electrocardiogram (ECG), Columbia-Suicide Severity Rating Scale, and physical examination
To investigate the effect of multiple doses of rifampicin on secondary PK parameters of multiple doses of balovaptan 10 mg qd and its major metabolites M2 and M3 at steady state in healthy subjects	Balovaptan and metabolite M2 and M3: t_{max} ; metabolite to parent ratio; any other parameter as appropriate
Tertiary/Exploratory	
To evaluate the plasma exposure of rifampicin 600 mg qd	Rifampicin C_{max} , AUC_{0-24h} , t_{max} , area under the plasma concentration-time curve from time zero to the last measurable plasma concentration time point (AUC_{0-last}) following 6 and 16 days of qd dosing of rifampicin, and any other parameter as appropriate
To investigate the relationship between the CYP3A4 genotype, among others ^a , and steady state balovaptan exposure, and the influence of the CYP3A4 genotype, among others, on the effect of rifampicin on balovaptan PK	The pharmacogenetics ^b of metabolizing enzymes, transferases, transporters, etc, possibly involved in the absorption, distribution, metabolism and excretion of balovaptan and its major metabolites (e.g., CYP3A and P-glycoprotein)

^aThe relationship between other genotypes and PK of balovaptan may also be explored.

^bResults may be pooled with data from other studies of balovaptan.

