#### 5.3.1 Tertiary/Exploratory Endpoints

Exploratory PK parameters for rifampicin following 6 and 16 days of qd dosing:

- $C_{max}$
- AUC0-24h
- $t_{max}$
- AUC0-last
- any other parameter as appropriate (see Table 1)

The pharmacogenetics of metabolizing enzymes, transferases, transporters, etc, possibly involved in the absorption, distribution, metabolism and excretion of balovaptan and its major metabolites (e.g., CYP3A and P-glycoprotein). Results may be pooled with data from other studies of balovaptan.

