## 7.0 Overview of Planned Analysis

### 7.1 Changes from Protocol

There are no changes from the protocol.

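### SAP Table 1 assigns rifampicin AUC0-last to Analysis Day 6 only, which omits the Day 16 value its endpoint requires; for the other rifampicin parameters, Day 16 is ambiguous.

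*SAP*

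**What the plan says.** The rifampicin exposure endpoint names four parameters: Cmax, AUC0-24h, tmax and AUC0-last. The protocol sets them "following 6 and 16 days of qd dosing of rifampicin, and any other parameter as appropriate" (Section 2, Table 1). SAP 5.3.1 repeats both days: "Exploratory PK parameters for rifampicin following 6 and 16 days of qd dosing".

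SAP 16.1.2 refers to SAP Table 1 for the parameter definitions. In that table:

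- AUC0-last is assigned to "Rifampicin/ Analysis Day 6".
- Cmax and tmax are assigned to "All analytes/ Analysis Day 10 (or Day 6 for rifampicin", closing with a bracket.
- AUC0-24h, lambda-z and half-life are assigned to "All analytes/ Analysis Day 10 (or 6 for rifampicin", again closing with a bracket.
- Ctrough is assigned to all analytes with no day stated.

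SAP 9.2.2 splits Study Period 2 into Analysis Period 2 (rifampicin alone, through Day 6) and Analysis Period 3 (the combination). It renumbers the latter: "For Analysis Period 3, the analysis day will also be adjusted by subtracting 6 from the study day". SAP 7.1 states: "There are no changes from the protocol".

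**The concern.** The AUC0-last row covers one of the two days in the endpoint. SAP 3.0 says that the SAP takes precedence over the protocol's statistical considerations and that substantial differences will be identified. None is identified here, and the row also disagrees with the SAP's own 5.3.1.

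The remaining rows raise a softer problem. With *or*, a programmer could take Day 6 as replacing Day 10 for rifampicin, and the Day 16 value of every parameter in those rows would then not be derived. Little else in the SAP would catch this: SAP 9.5 provides no table shells, and *Analysis Day 6* is printed without a period label although all three analysis periods contain a Day 6. The PK parameter dataset is to be double programmed (SAP 9.2.4.1), so two programmers could resolve the wording differently.

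At stake are the pre-specified rifampicin exposure parameters on study Day 16, the day on which the balovaptan test profile is taken.

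**Working it through.** **Inputs.** Endpoint days 6 and 16 (Protocol Section 2, SAP 5.3.1). Rifampicin profiles from the Day 6 and Day 16 doses of Study Period 2, each running to 24 hours (Protocol Appendix 2, SAP Appendix 3). Combination dosing on study Days 7 to 16 (SAP 6.0). Renumbering rule: analysis day = study day − 6 in Analysis Period 3 (SAP 9.2.2). Row assignments from SAP Table 1.

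**Step 1: reproduce the SAP's day range.** First combination day: 7 − 6 = 1. Last: 16 − 6 = 10. This agrees with "Thus, Period 3 will have Analysis Days 1 to 10". Study Day 16 is therefore Analysis Day 10 of Analysis Period 3.

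**Step 2: can the AUC0-last row reach study Day 16?** Analysis Day 6 falls in three periods:

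- Analysis Period 1: balovaptan alone, with no rifampicin given.
- Analysis Period 2: study Day 6 of Study Period 2, the rifampicin-alone profile.
- Analysis Period 3: study day 6 + 6 = 12, on which no rifampicin is sampled.

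Only the Analysis Period 2 meaning has data behind it. No reading of the row gives Day 16.

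**Step 3: count the endpoint values.** Four named parameters × 2 days = 8.

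| Parameter | Day 6 | Day 16, *or* read as covering both days | Day 16, *or* read as substitution |
|---|---|---|---|
| Cmax | yes | yes | no |
| tmax | yes | yes | no |
| AUC0-24h | yes | yes | no |
| AUC0-last | yes | no | no |

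Covered: 4 + 3 = 7 of 8 on the first reading, and 4 + 0 = 4 of 8 on the second. One value is missing on either reading, and 7 − 4 = 3 depend on the reader. Lambda-z and half-life share the ambiguous wording but are not among the four named parameters, so they are outside the count.

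**The case against.** A reader might infer that the Day 16 half of the whole rifampicin endpoint is dropped. The documents do not support that. Rifampicin is one of the four analytes in SAP 16.1.1, so all analytes on Analysis Day 10 can include rifampicin on study Day 16. Analysis Period 2 ends at Day 6 and has no Day 10, so the bracket is naturally read as supplying the profile day for rifampicin alone. That reading fits the renumbering, the sampling schedule and the by-treatment parameter summaries of SAP 16.2.2, since rifampicin is given in both Treatment I and Treatment S+I. This part of the objection stands: those rows are unclear, not shown to be wrong.

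A reader might also infer that the Day 16 samples (9 time points × 16 subjects = 144) go unused, or that the trial could not show inducer exposure on the day of the test profile. Neither follows. SAP 16.2.1 and Appendix 4 (Table 14.2.5 and the rifampicin figures) provide for rifampicin concentrations to be summarized by treatment and time point, plotted and listed. The Ctrough row has no day limit, so the 24-hour sample after the Day 16 dose enters a parameter even if *or* means substitution. Nor do the documents say that two days were chosen to compare rifampicin alone with rifampicin plus balovaptan; the stated objective is only to evaluate rifampicin exposure.

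Finally, AUC0-last may add little. Sampling ends at 24 hours, so if the last sample is quantifiable, AUC0-last and AUC0-24h cover essentially the same interval. If it is not, they can differ, because SAP 16.2.2 sets unquantifiable values after tmax to missing. The quantification limit is not given, so the documents do not settle how often that would occur. This limits the consequence of the omission but does not remove the contradiction with SAP 5.3.1.

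**Conclusion.** The point holds for AUC0-last. SAP Table 1 omits the Day 16 value that the protocol and SAP 5.3.1 both specify, and the SAP declares no change. For Cmax, tmax and AUC0-24h, and for lambda-z and half-life, the wording is ambiguous; the reading that covers both days is the more natural one.

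The size is minor: one of eight exploratory values lost for certain and three open to interpretation. No model or test is planned on rifampicin parameters, and the mixed-model comparison for the primary endpoints uses none of them. Because SAP 5.3.1 keeps both days, a slip in the table is a more likely explanation than a decision to drop part of the endpoint, though the documents do not say. The conclusion assumes that Table 1 is programmed as printed, as SAP 16.1.2 directs.

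**What to change.** In SAP Table 1, split the analyte and day column:

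- Rifampicin Cmax, tmax, AUC0-24h, AUC0-last, lambda-z and half-life: Analysis Period 2 Day 6 and Analysis Period 3 Day 10.
- Balovaptan, M2 and M3, for the parameters that apply to them on a profile day: Analysis Day 10 of Analysis Periods 1 and 3.

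If omitting the Day 16 AUC0-last is intended, say so in SAP 7.1 and bring SAP 5.3.1 into line. Either way the cost is a wording change in the SAP before database lock. The Day 16 samples are already scheduled, so no additional sampling is needed, and restoring Day 16 only brings the table back to the protocol.
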